## Overall design

UP0073 is a randomized, 2-part single-dose crossover Phase 1 study. A study overview of UP0073 is provided in [Figure 1-1](#).

The primary objective of Part A is to estimate the relative bioavailability of 2 new UCB0599 formulations (180mg film-coated tablet containing **CCI** with or without encapsulation) versus the current clinical formulation (2x90mg granules in capsule) under both normal and elevated gastric pH conditions. This portion of the study is an open-label, randomized, 2 in-series crossover substudies, each with a fixed sequence complete block design of 3 treatment periods in healthy male and female participants. The secondary objective is to evaluate the safety and tolerability of a single dose UCB0599 alone under normal and elevated gastric pH. Other objectives are to further evaluate the PK of UCB0599 and its metabolites (**CCI**) after a single-dose UCB0599 alone and co-administrated with esomeprazole. See Section 3 for more details on the objectives and endpoints of the study.

Part B of this study is an ethnobridging study evaluating the safety, tolerability, and PK of a single oral dose of UCB0599 at 3 dose levels (90mg, 180mg, and 360mg) under normal gastric pH conditions in healthy participants of Japanese and Chinese origins. Each group of ethnic origin (N=15 total for each) will be randomized to a 4-treatment, 6-sequence, 2-period crossover study using UCB0599:placebo in a 4:1 ratio, as shown below and in the Study Schema (see Section 1.2). Sequences 3 and 4 will only commence after Sequences 1 and 2 have been completed for all 5 participants; Sequences 5 and 6 will only commence after Sequences 3 and 4 have been completed for all 5 participants, allowing the Safety Monitoring Committee (SMC) review to be carried out before the start of Sequence 5.

- Sequence 1: placebo 90mg, followed by placebo 180mg (N=1)
- Sequence 2: UCB0599 90mg, followed by UCB0599 180mg (N=4)
- Sequence 3: placebo 180mg, followed by placebo 360mg (N=1)
- Sequence 4: UCB0599 180mg, followed by UCB0599 360mg (N=4)
- Sequence 5: placebo 360mg, followed by placebo 90mg (N=1)
- Sequence 6: UCB0599 360mg, followed by UCB0599 90mg (N=4)

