### **9.5 Planned safety and other analyses**

#### **9.5.1 Safety analyses**

Unless stated otherwise, all safety analyses will be performed on the SS.

All AEs will be coded using the most recent Medical Dictionary for Regulatory Activities (MedDRA®) and characterized as pretreatment and treatment emergent according to the intake of the study medication.

The occurrence and incidence of TEAEs will be summarized by MedDRA system organ class (SOC), HLT, and preferred term (PT), and by treatment and ethnic group (for Part B only). The occurrence and incidence of TEAEs will also be summarized by maximum event intensity and by relationship to the study medication. Adverse events will be categorized by severity (mild/moderate/severe). All AEs will be listed and will include actions taken for each AE, the time of onset of the AE after dosing, and the duration of each AE. Adverse events leading to discontinuation and SAEs will also be summarized by treatment group and ethnic group.

Laboratory variables and changes from Baseline will be summarized by time point and will be presented by treatment and ethnic group. For categorized values according to the reference range, shift tables from Baseline (Day -1, or Day 1 prior to first treatment) to each post-Baseline

time point will be presented for selected variables to be defined in the SAP. Values outside the reference range will be flagged in the listings.

Vital sign variables (SBP and DBP, pulse rate, respiration rate, and body temperature) and changes from Baseline (Day -1, or Day 1 prior to first treatment) will be summarized by time point and will be presented by treatment and ethnic group.

Single 12-lead ECGs will be recorded at each time point as noted in the study Schedule of Activities (Section 1.3). Descriptive statistics will be presented for ECG values and changes from Baseline (Day -1, or Day 1 prior to first treatment) over time.

See Section 9.8 for details on planned interim analyses and data monitoring.

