5.1.1.4 Definition of Analysis by Variables

Table 5-3: Definition of Analysis by Variables for Part A

Term	Variables
Sequence	Sequence 1 (ABC)
	Sequence 2 (ACB)
	Sequence 3 (BCA)
	Sequence 4 (BAC)
	Sequence 5 (CAB)
	Sequence 6 (CBA)
Formulation	180mg (90mg x 2 granules in capsule)
	180mg non-encapsulated tablet containing PPD
	180mg encapsulated tablet containing PPD
Gastric condition	Normal gastric pH
	Elevated gastric pH

Note: A: 180mg (90mg x 2 granules in capsule) current clinical formulation (reference formulation); B: 180mg non-encapsulated tablet containing PPD ; C: 180mg encapsulated tablet containing PPD .

Table 5-4: Definition of Analysis by Variables for Part B

Term	Variables
Sequence	Sequence 1 (C=1, J=1; 90mg → 180mg)
	Sequence 2 (C=4, J=4; 90mg → 180mg)

Table 5-4: Definition of Analysis by Variables for Part B

Term	Variables
	Sequence 3 (C=1, J=1; 180mg → 360mg)
	Sequence 4 (C=4, J=4; 180mg → 360mg)
	Sequence 5 (C=1, J=1; 360mg → 90mg)
	Sequence 6 (C=4, J=4; 360mg → 90mg)
Dose level	Pooled Placebo
	90mg
	180mg
	360mg
Participant group	Japanese participants
	Chinese participants
	Part A healthy participants under normal gastric pH condition on the formulation chosen for Part B

C=Chinese participants; J=Japanese participants.

Table 5-5: Analysis Performed by “by Variables”

Analysis	Part A by Variable	Part B by Variable
Disposition	Sequence	Sequence
Medical History		
Concomitant Medications		
Important Protocol Deviations		
PK Concentration	Formulation and gastric condition	Dose level and participant group
Adverse Events	Formulation	Dose level and participant group
Laboratory Values	Time Point and Sequence	Time Point Sequence
Vital Signs		
ECG		

ECG= electrocardiogram; PK=pharmacokinetic.

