Study discontinuation due to AEs will be tabulated using the RS, separately for Part A and Part B. Each table will present the number and percentage of participants who discontinued the study due to AE by treatment sequence.

By-participant listings of participant who did not meet study eligibility criteria will be presented by study part and treatment sequence, using the ASPS. The listing will include inclusion criteria that were not met and the exclusion criteria that were met.

By-participant listings of participant disposition will be provided using the ASPS, by study part and treatment sequence. The listings will include:

- Study termination/completion status
- Date of informed consent
- Date of randomization
- Date and time of first study treatment (first start date and time)
- Date and time of last study treatment (last stop date and time)
- Date of last contact

- Date of premature study termination for successfully screened participants dropping out of the study.
- Date of screen failure for screen failure participants (based on the last screening visit in case of rescreen)
- Primary reason for premature study termination
- Primary reason for screen failure (Based on the last screening visit in case of rescreen)

By-participant listings of participant inclusion in each analysis set will be presented by study part and sequence, using the ASPS.

By-participant listings of study discontinuation will be presented by study part and sequence, using the RS.

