Adverse events will be assigned to Treatment Periods, based on the onset date/time of the AE. Assignment to Treatment Periods will be done after missing dates have been imputed as described above. AE will be assigned to a treatment based on the treatment received in the Treatment Periods as given in [Table 5-8](#).

Table 5-8: AE Treatment Period Assignment

Study Part	Period	Start	End
Part A	Treatment Period 1	Start date is on or after administration of treatment in Treatment Period 1	Prior to administration of treatment in Treatment Period 2
	Treatment Period 2	Start date is on or after administration of treatment in Treatment Period 2	Prior to administration of treatment in Treatment Period 3
	Treatment Period 3	Start date is on or after administration of treatment in Treatment Period 3	Prior to administration of treatment in Treatment Period 4
	Treatment Period 4	Start date is on or after administration of treatment in Treatment Period 4	Prior to administration of treatment in Treatment Period 5
	Treatment Period 5	Start date is on or after administration of treatment in Treatment Period 5	Prior to administration of treatment in Treatment Period 6
	Treatment Period 6	Start date is on or after administration of treatment in Treatment Period 6	
Part B	Treatment Period 1	Start date is on or after administration of treatment in Treatment Period 1	Prior to administration of treatment in Treatment Period 2
	Treatment Period 2	Start date is on or after administration of treatment in Treatment Period 2	

The following summaries will be provided for Part A by formulation and for Part B by dose level and group:

- Incidence of TEAEs – Overview
- Incidence of TEAEs
- Incidence of Serious AEs
- Incidence of TEAEs leading to discontinuation
- Incidence of TEAEs by maximum intensity
- Incidence of TEAEs by relationship to study medication

AEs will be presented as “number of participant (percentage of participant) [number of events]”. In this style of output, “[number of events]” will include all cases of an AE including repeat occurrences in individual participant, while “number of participant” will count each participant only once.

AEs will be presented by system organ class (SOC), high level term (HLT) and preferred term (PT) in a frequency table, giving the number of events, the number of participants, and the percentage of participants who experienced the event. Participants with multiple AEs are only counted once within each PT, each HLT and within each SOC.

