5.5.3.2.1 Vital Sign Values Over Time

The vital sign variables and changes from Baseline will be summarized using descriptive statistics for Part A by time point, gastric condition ,and formulation, and for Part B by time point, dose level, and participant group. A listing will be provided for the SS.

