5.5.3.3.1 Electrocardiogram Values Over Time

The electrocardiogram results and changes from Baseline will be summarized using descriptive statistics for Part A by time point, gastric condition, and formulation, and for Part B by time point, dose level, and participant group. A by-participant listing will be provided for the SS.

The following cut-points in QTcF based on the mean of the triplicate data will be summarized categorically (number and percentage of participants).

For observed data:

- <450 msec
- ≥ 450 to <480 msec
- ≥ 480 to <500 msec
- ≥ 500 msec

For change from Baseline in QTcF:

- <30 msec
- ≥ 30 to <60 msec
- ≥ 60 msec "

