6.1.6 AEs of Special Interest

AE of special interest are:

- Hy's Law: Potential Hy's Law is defined as ≥ 3 xULN, ALT or AST with coexisting ≥ 2 xULN total bilirubin in the absence of ≥ 2 xULN ALP, with no alternative explanation for the biochemical abnormality (ie, without waiting for any additional etiologic investigations to have been concluded).
- Hypersensitivity reactions (such as rash, angioedema, or anaphylaxis).

A listing will be produced of Potential Hy's Law for the SS for Part A by treatment and for Part B by dose level and ethnic group.

A listing will be produced for Hypersensitivity reactions for the SS for Part A by formulation and for Part B by dose level and participant group using the following search strategy: Standardized MedDRA Queries (SMQ)='Hypersensitivity' (Broad) AND SMQ=Anaphylactic reaction (Broad).

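### No planned Part A adverse event table shows TEAE incidence under normal or elevated gastric pH, the two conditions named in the Part A secondary objective

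*SAP*

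**What the plan says.** The protocol synopsis, under Overall design, states for Part A: "The secondary objective is to evaluate the safety and tolerability of a single dose UCB0599 alone under normal and elevated gastric pH". Protocol Table 3-1 and SAP Table 1-1 give the secondary endpoints as the incidences of TEAEs, of serious TEAEs and of TEAEs leading to withdrawal. The text of the secondary-objective cell is missing from both tables in the copy we worked from, so the wording of the objective rests on the synopsis sentence.

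SAP section 5.5.2 sets the grouping: "The following summaries will be provided for Part A by formulation and for Part B by dose level and group". Six summaries follow: overview, all TEAEs, serious events, events leading to discontinuation, maximum intensity, and relationship to study medication. A participant with several events counts once. The adverse event row of SAP Table 5-5 likewise gives formulation alone for Part A.

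SAP Table 5-3 defines formulation (three levels) and gastric condition (two levels) as separate by-variables. Table 5-5 uses both for PK concentrations: "Formulation and gastric condition". Section 5.5.3.2.1 uses both for vital signs: "The vital sign variables and changes from Baseline will be summarized using descriptive statistics for Part A by time point, gastric condition", followed by formulation.

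**The concern.** The objective names two conditions, and the tables that carry its endpoints show neither. Someone who follows the SAP to the letter will produce columns for capsule, tablet and encapsulated tablet. A reader of those tables cannot find the TEAE incidence for UCB0599 given with esomeprazole, or given without it.

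The setting makes that question a practical one. Protocol section 4.2 puts the share of Parkinson's disease patients on acid-reducing agents at about 25%, and Part A is the part of this study that gives the drug both ways. The incidences would have to be rebuilt outside the planned outputs.

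**Working it through.** There is no plan figure to reproduce. The check sets the passages side by side.

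**1. Does formulation already include gastric condition?** No. Table 5-3 lists the two separately, and none of the three formulation labels mentions pH or esomeprazole. Where the SAP wants both (PK concentrations, vital signs) it names both.

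**2. What does a formulation column contain?** In the Part A design table (protocol Table 1-1, SAP Table 1-3) each sequence repeats its order: ABC is followed by ABC, and so on. A participant who completes takes each formulation twice, once in Periods 1-3 without esomeprazole and once in Periods 4-6 with it. Under the counting rule, a participant with an event only after the first dose, only after the second, or after both adds the same single count. The column cannot separate these cases.

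**3. How many of the six summaries show gastric condition?** All six fall under the one grouping rule, so 0 of 6.

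**4. Does another output fill the gap?**

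| Output | Part A grouping | Shows incidence by condition? |
|---|---|---|
| Discontinuation due to adverse events (SAP 5.2) | "Each table will present the number and percentage of participants who discontinued the study due to AE by treatment sequence" | No: every sequence contains both conditions |
| Hypersensitivity listing (SAP 6.1.6) | "A listing will be produced for Hypersensitivity reactions for the SS for Part A by formulation" | No |
| Potential Hy's Law listing (SAP 6.1.6) | Treatment, not defined further | No: a listing, not an incidence table |
| Registry tables (SAP 6.5) | None stated | Not specified |
| Adverse event listing (SAP 5.5.2) | Formulation | No: a listing |

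**5. Can the listing stand in?** Only with work. Its named fields include onset date and time but neither period nor gastric condition. Relative day restarts at each period's dose (SAP 5.1.1.1.1), so it does not identify the condition. Onset dates would have to be matched to the treatment administration listing in section 5.5.1. Partial dates are listed as reported, while period assignment uses imputed dates.

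**6. Would a plain split by period be right?** Not quite. Table 5-8 runs Period 3 from the Day 11 dose to just before the Day 19 dose, which is 18 - 11 + 1 = 8 calendar days (Days 11-18). Esomeprazole starts on Day 14 (protocol Table 1-3), so 18 - 14 + 1 = 5 of those 8 days are on esomeprazole. A plain split would label their onsets as normal pH.

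**7. Does this affect comparisons between formulations?** By design, no. Each column pools one dose per condition. The Period 3 formulation is C in ABC and BAC, B in ACB and CAB, and A in BCA and CBA, so each occupies that window in 2 of 6 sequences.

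**The case against.** The strongest reply is that the SAP follows the protocol. Section 9.5.1 asks for TEAEs by treatment, adding ethnic group only for Part B, and the Part A design table describes three treatments. The synopsis asks for safety to be evaluated under two conditions; it does not ask for a contrast between them. This stands in part. A reader might infer that the SAP contradicts protocol section 9.5.1; it does not. But an objective that names two conditions is not served by tables that show neither, even without a contrast.

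A second reply is that nothing is lost, because Table 5-8 assigns each event to a period and onset times are listed. That also stands, and it makes this a gap in reporting, not in data collection.

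A third concerns precedent. The ECG text is worded "summarized using descriptive statistics for Part A by time point, gastric condition, and formulation", and a reader might take that as further proof that safety data are split by condition. It does not help. In Part A, ECGs are scheduled only at screening, Day -1, Day 1 and the follow-up visit (Day 37 ± 2), which comes after the last esomeprazole dose on Day 33. No scheduled on-treatment ECG falls under elevated pH. Table 5-5 also lists vital signs and ECG by time point and sequence, against the text of section 5.5.3. The usable precedents are therefore the PK concentration row and the vital signs text.

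Finally, outputs follow the sponsor's standard table shells, which we have not seen. They might hold a split, but nothing in the SAP specifies one.

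**Conclusion.** The point holds as a reporting gap against a descriptive secondary objective. Its size is structural: 0 of 6 planned summaries, and no other specified adverse event table, give incidence under either condition. It rests on the synopsis wording of the objective and on the SAP text without the shells.

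Three stronger readings should be resisted:

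- **Bias.** A reader might infer that formulation comparisons are distorted. The design balances both conditions and the Day 14-18 window across formulations.
- **A numerical bound.** Participants who leave before Period 4 stay in the pooled columns with no dose under elevated pH. One might try to bound their number from 42 randomised and 36 completers. The 36 is an aim, not a limit, so the documents give no bound. The documents also give no event rates from which to size what the pooling hides.
- **An esomeprazole effect.** Split tables would not estimate one. Elevated pH always follows normal pH, so condition is confounded with time in the study.

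**What to change.** - In SAP section 5.5.2 and the adverse event row of Table 5-5, group Part A by formulation and gastric condition, with a total for each condition.
- Use as denominator the Safety Set participants dosed with that formulation under that condition. For each total, use those dosed with any formulation under that condition.
- Do not count onsets from the first esomeprazole dose to before the Period 4 dose as normal-pH events. Show them in one labelled esomeprazole lead-in column, not split by formulation, with participants who received at least one esomeprazole dose as denominator.
- Align the Part A listings in section 6.1.6 with this grouping.
- State that the split is descriptive because elevated pH always follows normal pH.

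The cost is SAP text, table shells and one added derivation flag for the lead-in. Part A columns go from 3 to 6 + 2 + 1 = 9, with fewer events in each. No new data are needed, and sample size and the PK analysis are unaffected.

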#### **4.1.2 Part B**

Part B of this study is an ethnobridging study evaluating the safety, tolerability, and PK of a single oral dose of UCB0599 at 3 dose levels (90mg, 180mg, and 360mg) under normal gastric pH conditions in healthy participants of Japanese and Chinese origins. Each group of ethnic origin (N=15 total for each) will be randomized to a 4-treatment, 6-sequence, 2-period crossover study using UCB0599:placebo in a 4:1 ratio, as shown below and in the Study Schema ([Figure 1-1](#)). Sequence 6 will only commence after Sequence 5 has been completed for all 4 participants. Sequences 3 and 4 (Cohort 3) will only commence after Sequences 1 and 2 (Cohort 2) have been

completed for all 5 participants; Sequences 5 and 6 (Cohort 4) will only commence after Sequences 3 and 4 have been completed for all 5 participants allowing the SMC review to be carried out before the start of Sequence 5.

- Sequence 1: placebo 90mg, followed by placebo 180mg (N=1)
- Sequence 2: UCB0599 90mg followed by UCB0599 180mg (N=4)
- Sequence 3: placebo 180mg, followed by placebo 360mg (N=1)
- Sequence 4: UCB0599 180mg, followed by UCB0599 360mg (N=4)
- Sequence 5: placebo 360mg, followed by placebo 90mg (N=1)
- Sequence 6: UCB0599 360mg, followed by UCB0599 90mg (N=4)

See Section 3 for more details on the objectives and endpoints of the study.

No participant will ever receive both UCB0599 and placebo, and therefore no intra-participant comparison will be possible; the crossover aspect of the Part B design refers to the dose level over 2 periods in order to limit the number of participants to be recruited into this study. This design will allow the collection of UCB0599 data at each dose level for 8 study participants of each ethnic origin and the collection of dose-matching placebo data for 2 study participants of each ethnic origin for each dose. Participants will be blinded to the treatment (ie, UCB0599 or placebo), but not to the dosage within a sequence.

Part B consists of the following periods (for a total duration of up to 45 days):

- A 28-day Screening Period (2 to 28 days before administration of study medication)
- 2 treatment periods (for a total duration of up to 10 days)

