5 STATISTICAL ANALYSIS

5.1 General Considerations

Statistical analysis and generation of tables, figures, and study participant data listings will be performed using SAS Version 9.4. The PK noncompartmental analysis will be performed using Phoenix WinNonlin® Version 8.0 or higher (Certara L.P., Princeton, NJ, USA) for PK parameters estimation.

A complete set of listings containing both all documented data and all calculated data will be generated by parts and treatment sequence, unless otherwise specified. Missing data will not be imputed, unless otherwise specified. Outlier detection and statistical analysis of outliers will not be performed.

Descriptive statistics will be displayed to provide an overview of the study results. For categorical endpoints, the number and percentage of study participants in each category will be presented. The denominator for percentages will be based on the number of study participants appropriate for the purpose of the analysis. For continuous endpoints, descriptive statistics will include number of study participants, mean, standard deviation (sd), median, interquartile range (IQR), minimum, and maximum. The descriptive statistics for plasma concentrations and PK parameters will be described in Appendix 2 (Section 6.2.1).

Unless otherwise noted, the denominator for percentages should be based on the number of participants included in the respective analysis set. For summaries of demographics and Baseline characteristics: summarize percentages based on all participants in the relevant analysis set and include a potential “Missing” category (corresponding to participants with missing data at the time of the variable being summarized) as the last row in the list of categories being summarized.

Percentages for frequency tables will be presented to 1 decimal place. If the percentage is 100%, do not present a decimal. If the percentage is 0, do not present the percentage. Typically, the % sign should be presented in the column header, but not with each individual value.

Decimal places for descriptive statistics will always apply the following rules, unless otherwise stated:

- “n” will be an integer
- Mean, sd, median, and IQR will use one additional decimal place compared to the original data
- Coefficient of variation (CV) [%] will be presented with one decimal place

- Minimum and maximum will have the same number of decimal places as the original value.

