5.5.2 Adverse Events

An Adverse Event is any untoward medical occurrence in a participant or clinical study participant, temporally associated with the use of study medication, whether considered related to the study medication.

Adverse events with start date/time prior to first treatment are defined as pre-treatment. These events will not be included in any tabulated summaries, but will be listed.

Treatment emergent AEs (TEAE) are all AEs starting on or after the date/time of first treatment and up to including 4 days after last treatment, or any unresolved event already present before administration of treatment that worsens in intensity following exposure to the treatment.

AEs with a start date after 4 days of last treatment are defined as post-treatment. These events will not be included in any tabulated summaries, but will be listed.

In case of missing or partially missing AE dates, the following rules will apply. Start and stop dates of AEs will be displayed as reported in the participant data listings (ie, no imputed values will be displayed in data listings).

The following rules will be applied for partial start dates and time:

- If only the month and year are specified and the month and year of the first treatment is not the same as the month and year of the start date, then use the 1st of the month, or the date of Screening if this is later (if the imputation results in an end date that is earlier than the start date, then use the 1st of the month). If time is missing, it will be imputed as 00:00 h
- If only the month and year are specified and the month and year of the first treatment is the same as the month and year of the start date, then use the date of the first treatment. If the imputed start date that is after the specified end date, then use the 1st of the month, or the date of Screening if this is later (if the imputation results in an end date that is earlier than the start date, then use the 1st of the month). If the imputed date is the date of treatment then time will be imputed as the start time of the treatment (ie, event will be regarded as treatment emergent)
- If only the year is specified, and the year of the first treatment is not the same as the year of the start date, then January 01 will be used. If time is missing, it will be imputed as 00:00 h

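### Part B adverse-event tables put a two-period Pooled Placebo percentage beside one-period dose percentages, so placebo incidence is expected to read too high relative to each dose

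*SAP*

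**What the plan says.** SAP 5.5.2 sets the layout of the incidence tables: "The following summaries will be provided for Part A by formulation and for Part B by dose level and group". SAP Table 5-5 gives the same split for Part B adverse events, "Dose level and participant group". SAP Table 5-4 defines four dose levels: "Pooled Placebo", 90mg, 180mg and 360mg.

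Events are attributed by period of onset: "AE will be assigned to a treatment based on the treatment received in the Treatment Periods as given in" Table 5-8. The treatment-emergent window is "Treatment emergent AEs (TEAE) are all AEs starting on or after the date/time of first treatment and up to including 4 days after last treatment". Within a column, "Participants with multiple AEs are only counted once within each PT, each HLT and within each SOC".

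On denominators, SAP 5.1 says that, unless noted otherwise, "the denominator for percentages should be based on the number of participants included in the respective analysis set". SAP 5.5.2 adds nothing specific to a column.

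In the six sequences (Protocol 4.1.2, SAP 1.2.2), Sequences 1, 3 and 5 are placebo in both periods and Sequences 2, 4 and 6 are two different active doses. Nobody receives both drug and placebo. Protocol 4.1.2 describes the design as allowing "the collection of dose-matching placebo data for 2 study participants of each ethnic origin for each dose". TEAE incidence is a primary safety endpoint of Part B (Protocol Table 3-2, SAP Table 1-2).

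**The concern.** Taken together, these rules give the columns different amounts of follow-up per person. A placebo participant is at risk of being counted in the one placebo column from the Day 1 dose until 4 days after the Day 6 dose. An active participant is at risk of being counted in a given dose column for one period only, about half that time. Because a person counts once per column, the placebo figure is a risk over two dosings and each dose figure is a risk over one.

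Placebo is the only concurrent control in these tables. Its percentage will be read directly against the dose percentages for a primary objective, and the unequal footing tends to make the drug look better than it is. No visible section of the SAP adds an adverse-event summary that is per-period, dose-matched, exposure-adjusted or for all active doses combined.

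**Working it through.** **Inputs.** Sequence sizes per origin, from Protocol 4.1.2 and SAP 1.2.2: 1 participant in each of Sequences 1, 3 and 5 (placebo); 4 in each of Sequences 2, 4 and 6 (active). The per-period TEAE probability q and the within-participant correlation ρ are not in the documents. I assume q = 10%, 20% and 30%, with ρ = 0, 0.5 and 1. All participants are taken to complete both periods.

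**Step 1: reproduce the plan's counts.** Each dose occurs in two active sequences (2 × 4 = 8) and two placebo sequences (2 × 1 = 2). The totals are 12 active + 3 placebo = 15, a ratio of 12:3 = 4:1. This matches the stated 8 active and 2 placebo per dose per origin.

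**Step 2: what each planned column contains, per origin.**

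| Column | Participants | Periods | Periods per participant |
|---|---|---|---|
| Pooled Placebo | 3 | 6 | 2 |
| Each dose | 8 | 8 | 1 |
| All active doses together (not planned) | 12 | 24 | 2 |

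**Step 3: expected percentages with no drug effect.** A dose column has expectation q. A participant followed for two periods has at least one event with probability 2q − P(event in both), where P(both) = q² + ρq(1 − q). With ρ = 0 this is 1 − (1 − q)². For q = 20% and ρ = 0.5: P(both) = 0.04 + 0.08 = 0.12, and 0.40 − 0.12 = 0.28.

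| q (each dose column) | Placebo, ρ = 0 | Placebo, ρ = 0.5 | Placebo, ρ = 1 |
|---|---|---|---|
| 10% | 19% | 14.5% | 10% |
| 20% | 36% | 28% | 20% |
| 30% | 51% | 40.5% | 30% |

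With independent periods the ratio is 2 − q: 1.9, 1.8 and 1.7. Only perfect correlation removes the excess.

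**Step 4: how often placebo strictly exceeds a given dose column with no drug effect.** This is exact enumeration of two independent binomials. As planned, they are Binomial(3, two-period risk)/3 and Binomial(8, q)/8. For placebo per participant-period, the first is replaced by Binomial(6, q)/6, which takes the six periods as independent.

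| q | Planned 3 vs 8, ρ = 0 | Planned 3 vs 8, ρ = 0.5 | Per participant-period 6 vs 8 |
|---|---|---|---|
| 10% | 45% | 36% | 40% |
| 20% | 65% | 54% | 49% |
| 30% | 71% | 59% | 48% |

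**Step 5: what this does to a real difference.** With assumed true per-period rates of 20% on placebo and 36% on drug and independent periods, both columns are expected to read 36%. With 20% and 40%, the chance that observed placebo incidence is at or above a given dose column is 43% as planned (3 vs 8). It is 21% with placebo per participant-period (6 vs 8) and 23% with Pooled Placebo against all active doses combined (3 vs 12).

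**The case against.** - **The display is descriptive.** SAP section 2 states no hypotheses, and the Part B group sizes rest on no formal calculation. The dosing-halt criteria in Protocol 7.1.5 turn on SAEs, severe events and other significant findings, not on this percentage. With 3 placebo participants, one person moves the column by 33 points. All of this stands and limits the consequence, but it does not put the two percentages on the same footing.
- **Pooling placebo follows the protocol.** The note to Protocol Table 1-2 lists placebo as one of four treatments, and Protocol 9.5.1 summarises TEAEs by treatment and ethnic group. This also stands. A reader might infer that the SAP abandons a promise of dose-matched placebo columns. The documents do not support that: Protocol 4.1.2 speaks of collecting such data, and the data are still collected.
- **The outputs allow reconstruction.** Each cell also shows the number of events, and the listings give onset times by dose level and group. A careful reader could rebuild per-period figures, but the printed percentages stay uncorrected.
- **Columns and denominators are not fully visible.** SAP 5.5.2 gives no column denominator, and the table shells are not in the documents. Participants per column (3 and 8) is the natural reading, not a stated one, and a combined active column in the shells cannot be ruled out. This is a reason to specify both in the SAP.
- **Independence is the least favourable case.** Two periods five days apart in one person are probably correlated. At ρ = 0.5, q = 10%, the planned layout puts placebo above the dose in 36% of trials, no more often than the 40% for independent participant-periods. The expected percentage is still inflated there (14.5% vs 10%).

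**Conclusion.** The point holds as a mismatch of observation time in a descriptive table for a primary safety endpoint. Followed as written, the SAP sets a two-period placebo risk beside one-period dose risks. With no drug effect and independent periods, the expected placebo reading is 1.7 to 1.9 times the dose reading for q between 10% and 30%. The ratio is 1.35 to 1.45 at a correlation of 0.5 and 1 at perfect correlation. These sizes rest on assumed q and ρ and on participants-per-column denominators.

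Three stronger readings should be resisted. The layout does not favour the drug in every trial: the bias is in expectation, and with 3 against 8 participants chance often reverses it. Larger probabilities can be obtained by combining the two origins (6 placebo vs 16 per dose), but the SAP tabulates by participant group, so that is not the planned table. Nor do the documents show that a drug effect would go unnoticed, since event counts, listings and the safety committee's review of accumulated data remain. This should be corrected; it does not affect sample size, error rates or data collection.

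**What to change.** In SAP 5.5.2, SAP Table 5-4 and the Part B adverse-event shells:

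1. Add an 'Any UCB0599' column (12 participants per origin, two periods each) and name it as the comparator for by-participant Pooled Placebo.
2. And/or report placebo incidence per participant-period (denominator 6 per origin) beside the single-dose columns.
3. State the denominator of every column.
4. If Pooled Placebo by participant stays next to the dose columns, add a footnote that it covers two dosing periods per participant and each dose column covers one.

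Dose-matched placebo columns (2 participants per origin) are unbiased in expectation but too sparse to lead with, so they would be supportive only.

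The cost is SAP wording and table shells. The drawbacks are an extra column and, for item 2, participant-periods that are not independent, so those percentages should stay descriptive.
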